### ***3.3.3.3 Handling of missing PK time***

If PK collection time is missing but PK result is available (include LLOQ), the collection time stamp will be estimated using the scheduled time and the time 0.

For example, if the value of PK at 24 hour post dose is not missing, but the collection Time of 24 hour post dose PK is unknown. Then the collection time 24 hour post dose PK will be estimated as: T0 + 24 hour.

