### 3.2.2 Per Protocol Time Points Vs Actual Time Points

Unless specified in the analyses section, actual blood sampling times, if available, will be used for individual figures while protocol times will be used for grouping summary.

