**Table 1 Protocol Defined Visit Schedule**

Procedure	Period:	Screening	Check-in a	Inpatient Observation	Outpatient Follow-up					Early Termination
	Day -28 to Day -2	Day -1	Days 0-3	Day 5	Day 7	Day 14	Day 21	Day 28	Day 28	
		0	See In-patient sch.	0	1	1	2	2		
	Tolerance (days)									

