**3.3.2 Trial conduct variables**

These include the visit dates and the study completion data of each participant. These variables are usually used for disposition or drug exposure summaries.

Reformatting maybe applied for display purpose but no additional calculation or transformation will be done before analyses unless specified in the analyses.

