#### **3.3.3.4.1 Time 0**

Time 0 is defined as the date and time of IP Administration.

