#### 3.3.3.4.5 $AUC_{0-t}$

The  $AUC_{0-t}$  of PK over time will be calculated using trapezoid rule and the actual time points. Missing data for the calculation of the AUC will be handled as followed:

1. If the reading for Time 0 is missing, it will be the assumed as 0.
2. If any reading between Time 0 and Tmax is missing:
  - a. It will be imputed with linear interpolation.
3. If any reading after CMax is missing:
  - a. If  $\lambda z$  is available, it will be imputed using the regression line obtained when estimate  $\lambda z$
  - b. If  $\lambda z$  is missing,  $AUC_{0-t}$  will be set as missing.

We will calculate the following  $AUC_{0-t}$

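### A PK sample with no recorded collection time is placed at its scheduled time without using the visit date, which can misplace an outpatient sample by 1 to 2 days in an AUC specified at actual times

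*SAP*

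**What the plan says.** SAP 3.3.3.3 covers a PK result that is available while its collection time is not: "the collection time stamp will be estimated using the scheduled time and the time 0". Its one example is an inpatient sample: "Then the collection time 24 hour post dose PK will be estimated as: T0 + 24 hour". SAP 3.3.3.4.1 fixes the anchor: "Time 0 is defined as the date and time of IP Administration". The rule is not limited to the inpatient period and has no step that consults the visit date.

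Four other places bear on it:

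- SAP 3.3.2 lists trial conduct variables: "These include the visit dates and the study completion data of each participant". Visit dates are therefore collected.
- SAP Table 1 gives outpatient tolerances of 0 days at Day 5, 1 day at Days 7 and 14, and 2 days at Days 21 and 28. The inpatient tolerances in Table 2 are 60 minutes or less.
- SAP 3.3.3.4.5 says that AUC0-t "will be calculated using trapezoid rule and the actual time points".
- SAP 3.2.2 sets the default: "actual blood sampling times, if available, will be used for individual figures while protocol times will be used for grouping summary".

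SAP 3.3.3.4.4 fits lambda-z by regressing log concentration on time over the readings after Tmax. It does not say whether that time is actual or scheduled.

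**The concern.** The only example is one where scheduled and actual time can differ by no more than an hour. At Day 21 or Day 28 they can differ by two days with the visit still in window. Protocol 7.2 adds that missing a window does not by itself remove a participant from the per-protocol analysis, so two days is not a hard ceiling. Read literally, the rule gives an off-schedule outpatient sample a nominal date when a better one is probably on file, and passes that date to an AUC meant to use actual times.

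The quantities at stake are secondary endpoints: AUC to Day 28, AUC to infinity and, through lambda-z, half-life, CL/F and Vz/F. Late samples close the widest trapezoids and carry the most leverage in the terminal regression. With three active participants per cohort, one profile is a third of a cohort mean.

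**Working it through.** The plan gives no figure of its own to reproduce. The inputs from the documents are the Table 1 tolerances, the linear trapezoid at actual times (SAP 3.3.3.4.5), the log-linear fit on all post-Tmax readings (3.3.3.4.4) and the tail as last reading divided by lambda-z (3.3.3.4.6).

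The following are assumed. PK is drawn at the outpatient visits (the sampling table is not shown; this is inferred from the planned AUC 0-21 Day and 0-28 Day). Sampling is at 0.25 to 72 hours and Days 5, 7, 14, 21 and 28. Kinetics are one-compartment with absorption rate 6 per day, half-life is 1 to 14 days, and readings are noise-free and quantifiable.

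**1. Largest in-window time error.** This equals the tolerance:

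- Day 5: 0 days
- Day 7: 1 day (1/7 = 14.3% of elapsed time)
- Day 14: 1 day (1/14 = 7.1%)
- Day 21: 2 days (2/21 = 9.5%)
- Day 28: 2 days (2/28 = 7.1%)

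**2. AUC to the last sample, Day 28 sample mis-stamped.** The last trapezoid is width × (C21 + Clast)/2. If the sample was drawn on Day 30 and stamped Day 28, the width falls from 9 to 7 days, so AUC changes by −(C21 + C30). If it was drawn on Day 26, the width rises from 5 to 7 days and AUC changes by +(C21 + C26).

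Take a 14-day half-life, with C(t) = ka/(ka − k) × (exp(−kt) − exp(−ka·t)) and k = ln 2/14. Then C21 = 0.3565, C30 = 0.2283 and C26 = 0.2783.

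- Late: −0.5848/15.6963 = −3.7%
- Early: +0.6348/14.6517 = +4.3%

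| Half-life (days) | Drawn 2 days early | Drawn 2 days late |
|---|---|---|
| 1 | +0.0% | −0.0% |
| 4 | +0.65% | −0.55% |
| 7 | +2.2% | −1.8% |
| 14 | +4.3% | −3.7% |

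If Days 21 and 28 both shift the same way, the extremes at 14 days are +6.1% and −5.3%.

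Part of this change is the end of the interval moving with the stamp. If the program cut AUC 0-28 Day at Day 28 by interpolation (the SAP does not say), the late case would be smaller. Interpolated C28 = 0.3565 + (7/9)(0.2283 − 0.3565) = 0.2568. The Day 21 to 28 area is 7 × (0.3565 + 0.2568)/2 = 2.147, against 7 × (0.3565 + 0.2283)/2 = 2.047 as stamped. The difference of about −0.100 on 15.211 is −0.7%.

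**3. Lambda-z, if fitted on actual times.** With post-Tmax points on Days 1, 2, 3, 5, 7, 14, 21 and 28, the mean day is 81/8 = 10.125 and the sum of squares about it is 1509 − 81²/8 = 688.875. A shift of 2 days at day d changes the slope by the fraction 2(d − 10.125)/688.875, whatever the half-life.

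- Day 28 alone: 2 × 17.875/688.875 = 5.2%. Half-life changes by 1/1.052 − 1 = −4.9% (late) or 1/0.948 − 1 = +5.5% (early).
- Days 21 and 28 together: 2 × (17.875 + 10.875)/688.875 = 8.3%. Half-life changes by −7.7% (late) or +9.1% (early).

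Across half-lives of 1 to 14 days, with the post-Tmax set that each profile gives, half-life changes by 4.5% to 5.5% for Day 28 alone and by 7.2% to 9.1% for both.

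**4. With the date kept.** If only the clock time is imputed, for example at midday, the error is at most 12 hours, against 1 or 2 days.

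**The case against.** The case against has several parts, and most of them stand.

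- **Lambda-z.** A reader might infer that lambda-z is specified at actual times because AUC is. SAP 3.3.3.4.4 says only time. If the regression runs on scheduled times, the rule does not affect lambda-z at all. The lambda-z figures are therefore conditional. The AUC effect does not depend on them.
- **A larger terminal error.** A fit on Days 14, 21 and 28 alone would move by 2 × 7/98 = 14.3%. The SAP does not fit that way: it uses every reading after Tmax, and SAP 3.3.3.2 keeps values below quantification at half the limit.
- **Overwriting a known date.** A reader might infer that the SAP orders a recorded draw date to be replaced. The rule does not say whether collection time means the clock time or the whole date and time, and SAP 3.3.2 does not say that the visit date is the draw date. A programmer could keep the date. The text neither requires nor suggests it, so two programmers could differ.
- **Visibility.** SAP 3.3 already has original and calculated values shown in listings, so an imputed time should largely be visible. No new listing rule is needed.
- **Rarity.** Several conditions must coincide: an outpatient sample, a result without a time, a known date and an off-schedule visit. Protocol 7.2 gives PK timing priority, and nothing suggests that missing times are expected.

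These points shrink the concern. They do not supply the missing date step.

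**Conclusion.** The point holds as a minor one. SAP 3.3.3.3 suits inpatient samples but is written for all samples, and at outpatient visits it can add an avoidable timing error of up to 1 day (Days 7 and 14) or 2 days (Days 21 and 28) within window. For one Day 28 sample that is about 0% to 4% on AUC to the last sample over assumed half-lives of 1 to 14 days. If lambda-z uses actual times, lambda-z and half-life move by about 5%, or about 7% to 9% with both late samples shifted the same way. With three similar active profiles, one affected participant moves a cohort mean by about a third of that: 4.3/3 = 1.4% for AUC and 5.5/3 = 1.8% for half-life.

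The documents do not support reading this as a general fault in the PK analysis. Samples with a recorded time are untouched, and grouped summaries use protocol times by design. One related loose end is that SAP Table 3 names a Day 22 visit where Table 1 has Day 21. If 22 were taken as the scheduled day, the in-window error for that sample could reach 22 − 19 = 3 days.

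**What to change.** In SAP 3.3.3.3, state three steps:

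1. If the date of the draw is recorded, keep it and impute only the clock time. If it is not, use the date of the visit at which the analysed sample was taken, including a repeat visit.
2. Use time 0 plus scheduled time only when the date is also missing.
3. Name the clock time to be imputed, for example midday.

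In SAP 3.3.3.4.4, state that lambda-z uses the same actual times as AUC. Correct the Day 21/Day 22 label in Table 3 at the same time.

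The cost is a few sentences and a small change to one derivation, with no new data. Two small burdens remain. A clock-time error of up to about half a day persists. Where a visit was repeated, the right date must be identified, because SAP 3.2.3.1 leaves dates and laboratory transfers to case-by-case judgement.

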### ***3.3.3.4 PK Parameters***

The following PK parameters will be developed directly from the PK data.

- PK parameters will only be calculated or evaluated for participants who receives EXT608 dose. PK parameters will not be calculated for placebo participants.

#### **3.3.3.4.1 Time 0**

Time 0 is defined as the date and time of IP Administration.

#### **3.3.3.4.2 The Maximum (CMax)**

CMax is the maximum PK readings from time 0 to the last PK measurement.

- In a “No Peak” case, this will be set as missing.

#### **3.3.3.4.3 Time to Maximum (TMax)**

## EXTBIO EXT608-101 Statistical Analysis Plan, V2, 2023-JULY-04

Tmax is the minutes, from time 0, to the time when CMax is reached the first time.

- In a “No Peak” case, this will be set as missing.

#### 3.3.3.4.4 Terminal rate constant $\lambda z$

Terminal rate constant  $\lambda z$  is needed before we estimate  $AUC_{0-t}$ . Since we are expecting the terminal PK will have an exponential decline,  $\lambda z$  is estimated by:

- Find the PK after TMax
  - If there only 1 or 0 available PK readings after PK Tmax, then  $\lambda z$  will be set as missing.
- Do a regression of log-transformed PK vs Time
- $\lambda z$  is  $-1 * (\text{slope from this regression})$
- In a “No Peak” case,  $\lambda z$  will be set as missing

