### 3.2 Trial schematic

### **3.3 Design rationale**

#### **3.3.1 Population**

PK modeling of various approaches to extend the half-life of compounds in animals is generally not a good predictor of half-life in humans. Knowledge of single dose PK and indications of PD in humans are usually sufficient to model multiple dose PK accurately and with reasonable precision, and can give good indications of plasma drug concentrations. This enables the accurate determination of target dose range for therapeutic effect and therefore guides optimal design choice for studies in patients with hypoparathyroidism.

The safest population in which to obtain the single dose PK is healthy participants.

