## EXTBIO EXT608-101 Statistical Analysis Plan, V2, 2023-JULY-04

**3.3.3.4.7 Time to Half-Maximal PK, Both Early and Late ( $t_{Half,early}$  &  $t_{Half,late}$ )**

$T_{half,early}$  is the time in minutes, from time 0, to the time when PK rises to half way to the maximum. It is calculated as followed:

- $T_{half,early} = \text{Time corresponding to } \frac{C_{Max}}{2} \text{. } t_0$ , linear interpolation may be used if needed.
- If  $C_{Max}$  is missing,  $T_{half,early}$  will also be set as missing.

$T_{half,late}$  is the # of days, from  $T_{Max}$ , to the time when PK reduced to half way to the maximum.

Since we assume the PK is exponential decline,  $T_{half,late}$  is calculated as followed

- $T_{half,late} = \frac{\ln(2)}{\lambda z}$
- If  $\lambda z$  is missing,  $T_{half,late}$  will also be set as missing.

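### λz is fitted to every reading after Tmax with no terminal-phase rule, so half-life and the parameters built on it can be biased, in a direction the documents do not fix

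*SAP*

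**What the plan says.** SAP 3.3.3.4.4 gives a short recipe: "Find the PK after TMax", then "Do a regression of log-transformed PK vs Time", then take minus the slope as λz. No step picks out the terminal part of the curve, no fit criterion is set, and the sign of the slope is not checked. Apart from the no-peak case, λz is missing only under the condition "If there only 1 or 0 available PK readings after PK Tmax", so two readings suffice.

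The stated rationale is "Since we are expecting the terminal PK will have an exponential decline". SAP 3.3.3.4.7 makes the wider statement "Since we assume the PK is exponential decline". It describes the late half-life as running from TMax "to the time when PK reduced to half way to the maximum", but computes it as ln(2)/λz.

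The same λz is used in several other places:

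- AUC0-∞ adds the last reading divided by λz (3.3.3.4.6).
- CL/F is dose over AUC0-∞ (3.3.3.4.8).
- Vz/F is dose over λz times AUC0-∞ (3.3.3.4.9).
- For a reading missing after the peak, 3.3.3.4.5 says "it will be imputed using the regression line obtained when estimate" λz.

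SAP 3.3.3.2 sets readings below LLOQ to half the LLOQ (100 pg/mL by default). Nothing removes those values from the regression.

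**The concern.** The rationale is about the terminal phase, but the fit uses everything after the peak. The two agree only if decline is a single exponential from Tmax onward, which the documents do not establish for this subcutaneous product. Protocol 3.3.1 itself says that animal modelling of half-life extension generally predicts human half-life poorly.

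Half-life, λz, AUC0-∞, CL/F and Vz/F are named secondary outcomes (Protocol 2.2), and a longer half-life is the reason for the product (Protocol 1.2). Protocol 3.3.1 also says: "Knowledge of single dose PK and indications of PD in humans are usually sufficient to model multiple dose PK accurately". It does not say that this particular λz will be the input, but this is the half-life the study would report.

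**Working it through.** The documents give no value for λz, half-life or Vz/F, so there is no figure to reproduce. The check applies the SAP rule to profiles whose true half-life is known.

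**Inputs from the documents.** Inpatient times are 0.25, 0.5, 1, 1.5, 2, 4, 8, 12, 18 and 24 h (SAP Table 2). Outpatient visits are on Days 5, 7, 14, 21 and 28 (Protocol 3.1.6).

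**Assumptions.** There are inpatient samples at 48 and 72 h, PK is drawn at every listed time, there is no noise, and every sample to Day 28 is quantifiable. The kinetic values are assumed as well.

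**Two-phase decline.** C(t) = (1−f)·2^(−t/E) + f·2^(−t/T) − 2^(−t/A), up to a constant. Absorption half-life A = 1 h, early half-life E = 6 to 12 h, terminal half-life T = 72 to 120 h, terminal share of the intercept f = 0.1 to 0.3.

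Worked case: E = 12 h, T = 120 h, f = 0.1. The sampled Tmax is 4 h, which leaves 11 readings:

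| t (h) | 8 | 12 | 18 | 24 | 48 | 72 | 120 | 168 | 336 | 504 | 672 |
|---|---|---|---|---|---|---|---|---|---|---|---|
| ln C | −0.418 | −0.611 | −0.896 | −1.165 | −2.025 | −2.525 | −2.978 | −3.272 | −4.243 | −5.214 | −6.184 |

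- SAP rule: Sxy/Sxx = −4129.36/512,595.6 = −0.008056, so λz = 0.008056 per h. Half-life = 0.6931/0.008056 = 86.0 h. Ratio to true = 86.0/120 = 0.72.
- Last three points: slope = (−6.184 + 4.243)/336 = −0.005777. Half-life = 0.6931/0.005777 = 120.0 h. Ratio 1.00.
- The time from the peak to half of the peak on this curve is about 15.8 h. The description in 3.3.3.4.7, its formula (86.0 h) and the true terminal half-life (120 h) are thus three different quantities.

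At the other end (E = 6 h, T = 72 h, f = 0.3) the SAP slope is −0.010172. Half-life is 0.6931/0.010172 = 68.1 h and the ratio 68.1/72 = 0.95.

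Over the whole grid, half-life is 0.72 to 0.95 of true, against 1.00 for the last three points. Passing the absorbed dose through both phases by convolution gives 0.71 to 0.94. With exact AUC to the last sample, Vz/F is also 0.72 to 0.95 of true. AUC0-∞ is within 0.4% of true, so CL/F hardly moves when sampling runs this late.

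**One-phase decline.** C(t) = 2^(−t/T) − 2^(−t/A), up to a constant, with A = 1 to 24 h and T = 48 to 120 h. The half-life ratio is 1.00 to 1.04. The highest case is A = 24 h, T = 48 h: Tmax falls at 48 h, six readings follow, and the fitted half-life is 49.9 h, so 49.9/48 = 1.04. Absorption that continues past the peak flattens the early readings, so the fitted half-life is too long.

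**Imputed readings.** Remove the 24 h sample from the worked case.

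- The refitted SAP line has mean time 195.8 h, mean ln C −2.8365 and slope −0.007963. At 24 h it gives −2.8365 + 0.007963 × 171.8 = −1.468. Ratio to true = exp(−1.468 + 1.165) = 0.74.
- Log-linear interpolation between 18 and 48 h gives −0.896 + (6/30)(−2.025 + 0.896) = −1.122. Ratio = exp(−1.122 + 1.165) = 1.04.
- Over the two-phase grid, the line gives 0.72 to 1.11 of true and interpolation 1.04 to 1.17.

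**Sign check.** If every reading after Tmax is below a common LLOQ, 3.3.3.2 makes them all equal. The slope is then 0 and ln(2)/λz is undefined. With two readings of which the second is higher, λz is negative, and so are the half-life and the AUC extrapolation. The SAP sets λz to missing in neither case.

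**The case against.** The SAP states its assumption openly. It expects a single peak (3.3.3.1), and no document mentions a distribution phase. If decline is mono-exponential from Tmax, using every reading is correct. The parameters are descriptive: Protocol 8.3 rules out formal hypothesis testing, escalation rests on adverse events and serum calcium (Protocol 3.1.5), and individual concentrations are listed, so λz can be re-estimated later. All of this stands, and it limits the severity. It does not rescue the rule, because the assumption cannot be known before a first-in-human study and nothing in the SAP checks it.

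A reader might go further in three ways that the documents do not support:

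- *Half-life and Vz/F are biased low.* That needs an early phase steeper than the terminal one. Under one-phase decline the half-life ratio is never below 1.00.
- *Late-absorption samples steepen the slope.* They flatten it.
- *Half-life will appear to lengthen with dose, because low doses lose their late samples.* Dropping all samples after Day 7 does give 0.32 to 0.75 in the two-phase grid, but the SAP does not drop them. With half-LLOQ values kept in the fit, the ratio is 0.84 to 2.23 if Day 7 is the last quantifiable sample and 0.70 to 1.34 if it is Day 14. No dose trend in a known direction follows.

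**Conclusion.** The concern holds as a missing terminal-phase rule whose bias has no known sign. With all samples to Day 28 quantifiable, half-life is about 0.72 to 0.95 of true under the assumed two-phase kinetics and 1.00 to 1.04 under the assumed one-phase kinetics. Vz/F follows half-life in the two-phase case. AUC0-∞ and CL/F are exposed through the extrapolation, but barely affected when sampling reaches Day 28. The kinetic values and the PK draw times are assumptions, so these ranges are illustrations and not predictions for EXT608.

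The two-point minimum, the missing sign check and the mismatch between description and formula in 3.3.3.4.7 can be read directly from the text. Severity is should-fix.

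**What to change.** - **SAP 3.3.3.4.4:** fit λz to the terminal phase only, using at least the last three quantifiable samples after Cmax, with the number of points chosen by best adjusted R-squared. Leave values substituted under 3.3.3.2 out of this fit. Set λz, late half-life, AUC0-∞, CL/F and Vz/F to missing if λz is not positive or fewer than three points qualify.
- **SAP 3.3.3.4.5:** fill a missing reading that lies between two available post-Cmax readings by log-linear interpolation between them. Such a gap then no longer needs λz, so it need not make AUC0-t missing when λz is not estimable.
- **SAP 3.3.3.4.7:** define the late half-life as ln(2)/λz and delete the description based on half of the maximum.

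The cost is SAP wording and programming, with no new data. Some participants will have these parameters reported as not estimable, possibly more at the lowest doses, and each cohort has only three on active drug. The rule removes the bias only if quantifiable sampling reaches the terminal phase. If it stopped at Day 7, the last three points would still give 0.74 to 1.00 in the two-phase grid. They would give 1.33 under one-phase decline with a 24 h absorption and 48 h terminal half-life.

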#### 3.3.3.4.5 $AUC_{0-t}$

The  $AUC_{0-t}$  of PK over time will be calculated using trapezoid rule and the actual time points. Missing data for the calculation of the AUC will be handled as followed:

1. If the reading for Time 0 is missing, it will be the assumed as 0.
2. If any reading between Time 0 and Tmax is missing:
  - a. It will be imputed with linear interpolation.
3. If any reading after CMax is missing:
  - a. If  $\lambda z$  is available, it will be imputed using the regression line obtained when estimate  $\lambda z$
  - b. If  $\lambda z$  is missing,  $AUC_{0-t}$  will be set as missing.

We will calculate the following  $AUC_{0-t}$

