### 3.1.6 Individual Participant Schedule

A screening visit will take place within 28 days of dosing. Eligible participants for each cohort will be admitted to the Clinical Research Unit (CRU) 1 day prior to dosing and remain in the CRU through at least 72 hours after dosing for safety and PK assessments before discharge. The total confinement period will be 4 nights, unless extended for management of AEs at the discretion of the Investigator. The schedule of events while

inpatient is provided in [Section 7.1.1](#). Follow-up visits to the CRU will occur on/about days 5, 7, 14, 21 and 28. Participants will be monitored closely during the duration of the study for safety, PK, and PD assessments as described in [Section 3.2](#). The total duration of follow-up period may be modified in the final study design based on safety and PK data from non-clinical studies, anticipated PK/PD response and extended in individual participants as needed to observe their calcium levels return to concentrations deemed not needing further follow up.

Additional/Alternative PK/PD time points may be implemented if the Sponsor determines this is necessary to fully characterize the PK profile of EXT608.

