### 6.9.4 Pharmacokinetics (PK)

One 5 ml serum sample will be collected at the time points noted in [Section 7.1.1](#) and divided into 2 aliquots of 1ml each for determination of EXT608 concentrations. Samples will be shipped to the laboratory in batches, with one of the samples retained at the site in case of transfer problems.

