#### 3.3.3.4.6 $AUC_{0-\infty}$

$AUC_{0-\infty}$  is estimated as:

$AUC_{0-\infty} = AUC_{0-\text{last}} + AUC_{\text{last}}$ , where  $AUC_{\text{last}} = PK_{\text{last}}/\lambda z$ , and  $PK_{\text{last}}$  is the last available PK reading

- If  $\lambda z$  is missing, then  $AUC_{0-\infty}$  is set as missing.

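### The SAP's unqualified trapezoid rule, read as linear, overstates AUC(0-28d) by about 2-5% under its own exponential assumption; name a linear-up/log-down rule and settle trailing values below LLOQ in the same edit.

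*SAP*

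**What the plan says.** SAP 3.3.3.4.5 states that AUC(0-t) "of PK over time will be calculated using trapezoid rule and the actual time points". No linear, logarithmic or mixed variant is named.

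Four other SAP rules rest on exponential decline:

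- Lambda-z (3.3.3.4.4) is the slope of log concentration on time after Tmax: "Since we are expecting the terminal PK will have an exponential decline".
- The late half-life (3.3.3.4.7) is ln(2)/lambda-z: "Since we assume the PK is exponential decline".
- A missing reading after Cmax (3.3.3.4.5, item 3a) is filled from the log-linear fit: "it will be imputed using the regression line obtained when estimate" lambda-z.
- AUC(0-inf) (3.3.3.4.6) is AUC(0-last) plus PKlast/lambda-z, where PKlast "is the last available PK reading".

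CL/F and Vz/F (3.3.3.4.8 and 3.3.3.4.9) both divide by AUC(0-inf). SAP 3.3.3.2 sets any post-dose value below LLOQ to half of LLOQ, or to 100 pg/mL if the laboratory gives no limit.

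On timing, Protocol 3.1.6 has participants "remain in the CRU through at least 72 hours after dosing for safety and PK assessments before discharge", and then "Follow-up visits to the CRU will occur on/about days 5, 7, 14, 21 and 28". Protocol 6.9.4 leaves the PK draw times to the schedule in section 7.1.1, which cannot be read in the available text. SAP Table 4 asks for AUC to 7, 14, 21 and 28 days, which makes draws at those visits likely.

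**The concern.** The SAP uses an exponential curve for the tail and for missing late readings, but joins observed late readings with straight lines. After Day 3 the visits are 2, 2, 7, 7 and 7 days apart, so those lines may span long stretches of the curve. Two participants with the same true profile could also get different AUCs, depending on whether a late reading was observed or imputed.

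AUC(0-28d), AUC(0-inf), CL/F and Vz/F are secondary endpoints. Protocol 3.3.1 says, in general terms, that single-dose PK is usually enough to model multiple-dose PK. A bias from the integration rule does not shrink as participants are added.

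**Working it through.** The documents give no AUC, CL/F or half-life for EXT608, so there is no figure to reproduce. The check uses the SAP's formulas with stated assumptions.

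**One declining interval.** Let concentration fall from C1 to C2 = C1·exp(-λh) over a gap h.

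- Linear trapezoid: h(C1 + C2)/2.
- True area: (C1 - C2)/λ.
- Ratio: x·coth(x), with x = λh/2, which always exceeds 1.
- Logarithmic trapezoid: h(C1 - C2)/ln(C1/C2) = (C1 - C2)/λ, which is exact.

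For a half-life of 2 days, λ = 0.693/2 = 0.347 per day. With h = 2, x = 0.347 and the ratio is 1.040. With h = 7, x = 1.213 and the ratio is 1.45.

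| Half-life (days) | 2-day gap | 7-day gap |
|---|---|---|
| 0.5 | +57% | +385% |
| 1 | +15.5% | +146% |
| 2 | +4.0% | +45% |
| 4 | +1.0% | +12% |
| 7 | +0.3% | +4% |

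**Whole profile.** The large entries apply where little area remains, so the whole curve is what matters. Assumptions:

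- One compartment, first-order absorption.
- Samples at 0, 0.25, 0.5, 1, 1.5, 2, 4, 8, 12, 18, 24, 48 and 72 hours and Days 5, 7, 14, 21 and 28.
- No value below LLOQ.

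Percentage errors under the linear rule:

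| Terminal half-life (days) | AUC(0-28d), absorption half-life 2 h | AUC(0-28d), absorption half-life 6 h | CL/F, absorption half-life 6 h |
|---|---|---|---|
| 0.5 | +4.9 | +4.8 | -4.6 |
| 1 | +4.5 | +4.3 | -4.2 |
| 1.5 | +5.1 | +5.1 | -4.9 |
| 2 | +5.4 | +5.4 | -5.1 |
| 3 | +4.8 | +4.8 | -4.5 |
| 4 | +3.8 | +3.8 | -3.6 |
| 5 | +3.0 | +2.9 | -2.8 |
| 7 | +1.9 | +1.8 | -1.7 |
| 10 | +1.1 | +1.0 | -0.9 |
| 14 | +0.6 | +0.5 | -0.4 |

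An added 36-hour sample moves the peak only to +5.6%. Bi-exponential declines gave +2.8% to +4.8% for AUC(0-28d).

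**Where the error arises** (absorption half-life 2 h, percentage points of AUC(0-28d)):

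| Half-life (days) | Before Day 3 | Day 3 to Day 7 | After Day 7 |
|---|---|---|---|
| 0.5 | 3.77 | 1.07 | 0.03 |
| 2 | 0.15 | 1.10 | 4.13 |
| 7 | -0.05 | 0.09 | 1.88 |

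**Linear-up/log-down on the same profiles**, for terminal half-lives of 12 hours to 7 days: the AUC(0-28d) error is -0.9% to -0.1% at an absorption half-life of 2 h. It reaches -1.7% at 6 h and -2.3% at 12 h.

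**With the half-LLOQ rule switched on.** Here LLOQ is an assumed fraction of Cmax, absorption half-life is 2 h, and substituted values enter the AUC, lambda-z and PKlast.

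| LLOQ | Half-life | Quantity | Linear | Linear-up/log-down |
|---|---|---|---|---|
| 5% of Cmax | 1 day | AUC(0-28d) | +30% | +26% |
| 5% of Cmax | 1 day | CL/F | -29% | -27% |
| 5% of Cmax | 2 days | AUC(0-28d) | +16% | +13% |
| 10% of Cmax | 7 days | CL/F | +0.7% | +2.8% |

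Substituted values form a flat plateau across the weekly gaps. The integration rule cannot correct that.

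**The case against.** The strongest case for leaving this alone is materiality. With three active participants and an assumed between-participant CV of 20-40%, the standard error of a cohort mean is 20/√3 to 40/√3, or about 12-23%, well above a bias of at most about 5.6%. PK is mainly descriptive, escalation under Protocol 3.1.5 uses adverse events and serum calcium, and a bias common to all doses largely cancels in dose proportionality. A product designed for a long half-life may sit at 10-14 days, where the error is about 1% or less. All of this stands, and it keeps the point minor.

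The inputs are also partly inferred. Draws at every follow-up visit are likely but not confirmed, Protocol 3.1.6 allows added PK time points, and linear is the natural reading of the SAP wording rather than its stated rule. The size is therefore conditional.

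A reader might infer that the bias always runs one way, and that a logarithmic rule removes it at no risk. The documents do not support that. Under SAP 3.3.3.2, trailing half-LLOQ values can dominate the error, and in one case above CL/F was already overstated and the logarithmic rule alone made it worse. Values below LLOQ are plausible after a 4 µg starting dose. Nor do the 2- to 7-day gaps always drive the error: at a 12-hour half-life most of it arises before Day 3.

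**Conclusion.** The point holds as a minor one. The integration rule is unspecified and, read as linear, does not match the exponential decline that the SAP assumes everywhere else. AUC(0-28d) is overstated by about 2-5% for terminal half-lives of 12 hours to 7 days and by about 1% or less at 10-14 days; CL/F is understated by a similar amount.

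This rests on four assumptions: PK draws at the follow-up visits, values above LLOQ, a roughly exponential decline, and half-lives that the documents do not give. It does not support a claim that any dose decision or dose-proportionality conclusion would change. Where late values fall below LLOQ, the substitution rule matters more than the trapezoid variant, so the two need to be settled together.

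**What to change.** In SAP 3.3.3.4.5, specify the linear trapezoid on rising segments and the logarithmic trapezoid on declining segments, with linear wherever a value is zero or equals the one before it.

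In the same edit, amend SAP 3.3.3.2, 3.3.3.4.4 and 3.3.3.4.6 so that AUC(0-last), PKlast and the lambda-z regression all stop at the last quantifiable concentration, rather than carrying half-LLOQ values through the trailing visits. Also state how a fixed-horizon AUC such as 0-28 days is completed when that concentration falls earlier. Treating the trailing values as missing would let the existing item 3a fill them from the regression line.

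The cost is a few SAP sentences and a small programming change. Data collection is unaffected. The logarithmic rule should not be adopted without the LLOQ change.
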